# 3. LIST OF ABBREVIATIONS AND DEFINITIONS OF TERMS

Placebo	An inert or innocuous substance used especially in controlled experiments
	testing the efficacy of another substance (as a drug)
Doxycycline	Name of the study "drug" in this protocol. Consists of an adenovirus vector
	expressing the human vascular endothelial growth factor gene.
AE	Adverse event
FEV1	Forced expiratory volume over 1 second
FVC	Forced vital capacity
HRCT	High-resolution computed tomography
PFT	Pulmonary function test
COPD	Chronic Obstructive Pulmonary Disease
HIV	Human immunodeficiency virus
MMP	Matrix metalloproteinases
DLCO	Carbon monoxide diffusing lung capacity
CD4 count	T-cell count
TLC	Total lung capacity
EKG	Electrocardiogram
SGRQ	St. George's Respiratory Questionanire
САТ	COPD assessment test
Bronchoscopy	Procedure to examine the airways of the lungs
BAL	Bronchoalveolar lavage
BALF	Bronchoalveolar lavage fluid
ELF	Epithelial lining fluid
DGM	Department of Genetic Medicine
WCMC	Weill Cornell Medical College

#### **Study Period (years):**

Active study: 2 years Subject Participation: 24 weeks

#### **Objectives:**

*Primary:* To determine the safety, tolerability, and biologic effects of twice daily doxycycline for 6 months in HIV-infected subjects with COPD and/or emphysema.

*Secondary:* To characterize changes in FEV1, FVC, FEV1/FVC, DLCO over time; To characterizes change in respiratory symptoms over time (using the CAT COPD assessment test); To characterize change in BAL absolute cell number (AM, PMN, lymph); To characterize change in AM gene expression of MMPs and cytokines; To characterize change in BAL fluid MMP enzyme activity and cytokine levels; To characterize change in serum inflammatory markers (hsCRP, sIL-6, TNF-alpha, IL-1beta, procalcitonin); To determine doxycycline drug concentrations in serum, AM and ELF; To characterize change in quantitative bacterial burden in BAL fluid; To characterize frequency of doxycycline-resistant bacteria To describe adherence to study therapy by self-report and pill counts; To determine the incidence of non-elective hospitalization, classified as respiratory or non-respiratory; To determine the incidence of acute exacerbation of COPD (using the GOLD definition of change in symptoms requiring medication [we will use systemic steroids and/or antibiotics as the indicators]) To evaluate the role of biological mechanisms, such as oxidant stress, apoptosis, VEGF deficiency, etc., in relative gene expression of human alveolar macrophages and airway epithelial cells.

#### **Study Design:**

HIV-infected patients are at increased risk of COPD and emphysema may be accelerated in this population. While the pathogenesis of COPD in HIV-infected patients is almost certainly multifactorial, our preliminary data suggest that upregulation of MMPs may play a role in accelerating lung damage. Our overarching hypotheses are: (1) long-term doxycycline therapy will be safe and well tolerated; and (2) doxycycline will inhibit the activity of alveolar macrophage and epithelial lining fluid MMP. To determine this, we propose to conduct a randomized, double-blind, placebo-controlled pilot study of doxycycline 100 mg twice daily (2:1 doxycycline;placebo randomization) in 30 HIV-infected subjects with COPD and/or emphysema. We propose initially to conduct a pilot study as proof of concept of the biological effects of doxycycline, and to generate preliminary data that will facilitate the design of a larger Phase II clinical trial. For this study, the primary endpoint will be safety/tolerability, and secondary endpoints will include change in pulmonary function (FEV1) by spirometry, inhibition of MMP activity in a pan-MMP activity assay as well as individual MMPs assessed by gelatinase assays and doxycycline levels in serum, epithelial lining fluid and bronchoalveolar lavage cell pellets (consisting of alveolar macrophages, lymphocytes and some neutrophils).

Doxycycline (or matching placebo) will be given at a dose of 100 mg po twice daily for six months. This is a standard FDA-approved antibacterial dose for which there is abundant safety

data. While there are FDA-approved doses of doxycycline that are lower (e.g., 20-40 mg po daily for gingivitis or rosacea), we have selected a higher dose in this proof of concept trial in order to reduce the likelihood that we falsely conclude that the drug does not have the intended biological effects due to inadequate drug levels in the lungs. Pharmacokinetic data from subjects with cystic fibrosis support a 200 mg po daily dose of doxycycline to achieve appropriate lung levels.

Eligible subjects will have controlled HIV infection and a diagnosis of mild to moderate COPD and/or based on established criteria. Subjects will be randomized by the research pharmacist in a 2:1 fashion using permuted blocks of size 3 to receive doxycycline or placebo for 6 months and will undergo serial measures of lung function by spirometry as well as bronchoscopies at baseline and week 12 to collect specimens for translational studies aimed at characterizing the biological effects of the intervention. The bronchoscopy will be performed mainly as an outpatient procedure. The investigator may stop the procedure at any time if he/she feels that sufficient samples have been collected and/or it is not safe to continue the procedure. Subjects are expected to have an escort on the day of the bronchoscopy in order to undergo the bronchoscopy procedure. If the escort does not arrive or if no responsible adult is available to escort the subject home once the bronchoscopy procedure is complete, the subject will undergo observation by research staff until deemed stable. Follow-up calls will be performed one day (+/-3 days) and one week (+/-3 days) post-bronchoscopy. The randomization will be stratified on current versus former smoking status. The study is double-blinded, and only the research pharmacist will have knowledge of the treatment assignments, which is needed to dispense the study drug. Despite the pilot nature of this study, we have opted to conduct a randomized, placebo-controlled trial primarily to ensure that there is a control group to be able to interpret changes in biologic and physiologic endpoints that may vary based on the natural variation in the course of COPD and/or variability in the assays/assessments. We will randomize 2:1 in favor of active study drug to enable us to have a sufficient number of recipients of active drug within the constraints of a small study.

**Number of subjects (planned):** 30 subjects will be enrolled and will be randomized in a 2:1 fashion. Subjects for this study will be recruited from the referral base of the investigators from the population of individuals with COPD and documented HIV as defined by the protocol inclusion/exclusion criteria (see below).

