#### Exclusion Criteria:

- 1. Pulmonary infection, COPD exacerbation, or acute opportunistic infection within 30 days of entry
- 2. Conditions associated with increased sedation of bronchoscopy risk, including but not limited to Gold class 3 or 4 COPD, requirement for home oxygen, hypercapneic respiratory failure, poorly control hypertension
- 3. Known allergy/intolerance to doxycycline, atropine, or any local anesthetic
- 4. Inability to provide informed consent
- 5. Pregnant or lactating women
- 6. Men must agree not to attempt to make a woman pregnant of participate in sperm donation during the study and for 6 weeks after discontinuing the drug
- 7. End stage renal disease
- 8. Cirrhosis
- 9. INR greater than 1.4
- 10. Platelets less than 80,000
- 11. Any condition including active drug or alcohol use or dependence that, in the opinion of the site investigator, would interfere with adherence to study requirements or increase the risk of bronchoscopy
- 12. Active or planned participation in any other clinical trial or observational study without prior approval from the PI

**Endpoints:** The primary endpoint will be safety/tolerability, and secondary endpoints will include change in pulmonary function (FEV1) by spirometry, inhibition of MMP activity in a pan-MMP activity assay as well as individual MMPs assessed by gelatinase assays and doxycycline levels in serum, epithelial lining fluid and bronchoalveolar lavage cell pellets (consisting of alveolar macrophages, lymphocytes and some neutrophils).

**Statistical Considerations:** The overall sample size is 30 subjects, all of whom will be recruited at WCMC. We anticipate screening 70 subjects to randomize 30. The study investigates the safety/ tolerability (grade 2 or higher toxicity) of long-term use of doxycycline. A 20-30% rate of grade 2 or higher toxicity is expected. With 20 doxycycline recipients, we will have approximately 80% power (one-sided alpha = 0.05) to detect a true proportion of 20% (grade 2 or higher toxicity) while rejecting the null hypothesis of 45.5% or higher (in other words, ruling out the possibility of the event rate being any higher that 45.5%). Below are additional scenarios based on a true proportion of 5- 40% (P1), which demonstrate power greater than 80% for n = 20 doxycycline recipients under these assumptions.

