#### 12.1d. Definition of Relationship to Study Drug

The blinded Principal Investigator or medically qualified designee must review each AE and make the determination of relationship to study drug using the following guidelines:

**Not Related:** The event can be readily explained by other factors such as the subject's underlying medical condition, concomitant therapy, or accident, and no temporal relationship exists between the study drug and the event.

Unlikely: The event does not follow a reasonable temporal sequence from drug administration and is readily explained by the subject's clinical state or by other modes of therapy administered to the subject.

Possibly Related: There is some temporal relationship between the event and the administration of the study drug and the event is unlikely to be explained by the subject's medical condition, other therapies, or accident.

**Probably Related:** The event follows a reasonable temporal sequence from drug administration and cannot be reasonably explained by the known characteristics of the subject's clinical state.

Definitely Related: The event follows a reasonable temporal sequence from administration of the medication, follows a known or suspected response pattern to the medication.

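### A single block size of 3, printed in the protocol, lets one recognised placebo subject, or two recognised doxycycline subjects, reveal the rest of their block

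*Combined protocol and SAP*

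**What the plan says.** The Study Design part of the synopsis sets out the randomisation:

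- Ratio: "We will randomize 2:1 in favor of active study drug".
- Blocks: "using permuted blocks of size 3 to receive doxycycline or placebo for 6 months". No second block size is given, and nothing says that the size is withheld from site staff.
- Strata: "The randomization will be stratified on current versus former smoking status".
- Masking: "Doxycycline (or matching placebo) will be given at a dose of 100 mg po twice daily for six months", and "only the research pharmacist will have knowledge of the treatment assignments".

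Under Statistical Considerations: "The overall sample size is 30 subjects, all of whom will be recruited at WCMC". The same paragraph states the primary question: "The study investigates the safety/ tolerability (grade 2 or higher toxicity) of long-term use of doxycycline".

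On who judges events, Section 12.1d says: "The blinded Principal Investigator or medically qualified designee must review each AE", and asks that person to decide relatedness to study drug. Section 12.1c requires grading by the Division of AIDS table, with a four-level fallback scale, but names no grader. Section 13.6 has the principal investigators monitor safety monthly, on aggregate and blinded data, in place of the institutional board.

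**The concern.** A small fixed block lets knowledge of one assignment spread to others. At a single centre with two strata, staff can be expected to know each subject's smoking status and order of entry. With the size in print, they can then tell which subjects share a block.

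The documents leave two ways in which an assignment might become known:

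- Section 11.1 lists recognisable doxycycline effects such as photosensitivity and gastrointestinal events. These point to a doxycycline subject.
- Table I (footnote 5) and Table III schedule doxycycline blood levels at six visits. A post-baseline sample without drug would point to a placebo subject. The protocol does not say when the assays are run or whether results are kept from the investigators.

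A code break would be a third way, though none is described. What is at stake is the independence of judgements that feed a partly subjective safety outcome, with no independent adjudication described.

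**Working it through.** **Inputs.** Ratio 2:1, block size 3, two strata, 30 subjects, one centre (Study Design and Statistical Considerations). Blocks of 6 are the comparator. I assume that staff know entry order within each stratum and that the block is complete. D is doxycycline and P is placebo.

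**The plan's own figure.** The stated power is about 80% for 20 doxycycline recipients, true rate 20%, null rate 45.5%, one-sided alpha 0.05. The exact binomial test that rejects at 5 or fewer events gives 80.4%, with type I error 0.0505, so the figure reproduces. Block size does not enter it.

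**What one or two known assignments reveal.** A block of 3 has three sequences: DDP, DPD, PDD. A block of 6 (4 D, 2 P) has 15.

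| Known in the block | Question | Block of 3 | Block of 6 | No block information |
|---|---|---|---|---|
| One P | Is a given block-mate D? | 2/2 = 100% | 4/5 = 80% | 67% |
| Two D | Is a given other block-mate P? | 1/1 = 100% | 2/4 = 50% | 33% |
| One D | Is a given block-mate D? | 1/2 = 50% | 3/5 = 60% | 67% |

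**Upper bound on predictability.** Suppose that every earlier assignment in the block is known, and count the positions that are then forced.

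- Block of 3: DDP 1, DPD 1, PDD 2, total 4 of 9 = 44.4%.
- Block of 6: 26 of 90 = 28.9%.

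**The proposed mix.** Assume sizes 3 and 6 are equally likely and unknown to staff, and take the first three subjects of a stratum.

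- First subject known to be P. This has probability 1/3 under either size, so the sizes stay equally likely. The next two are both D with probability 1 in a block of 3 and 4/5 × 3/4 = 0.60 in a block of 6. The mix gives ½ × 1 + ½ × 0.60 = 0.80, against 1.00 now.
- First two known to be D. This has probability 1/3 under size 3 and 4/6 × 3/5 = 2/5 under size 6, so the sizes now have weights 5/11 and 6/11. The third is P with probability 5/11 × 1 + 6/11 × ½ = 8/11 = 73%, against 100% now.

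**Cost in balance.** The largest deviation from 2:1 in one stratum is:

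- Blocks of 3: a first subject on P gives 0 against 2/3 expected, a deviation of 0.67.
- Blocks of 6: two P first give 0 against 4/3, or four D first give 4 against 8/3, a deviation of 1.33.

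Over both strata the expected doxycycline count is 30 × 2/3 = 20, so the total deviation is a whole number. It is at most 2 × 0.67 = 1.33 with blocks of 3, hence 1 (19 to 21). It is at most 2 × 1.33 = 2.67 once blocks of 6 are used, hence 2 (18 to 22).

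**The case against.** The strongest reply is that the arithmetic is conditional on a recognition that the plan guards against. Placebo is matching, only the pharmacist holds the assignments, and nothing gives a probability that even one subject is recognised. This stands, and it rules out several stronger readings:

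- *A reader might infer that drug side effects expose placebo subjects.* They point to doxycycline subjects. One of those leaves each block-mate at 50%, so certainty by this route needs two correct recognitions in the same block.
- *A reader might infer that 44% of assignments are predictable in practice.* That figure assumes all earlier assignments in the block are known. It is a ceiling.
- *A reader might infer that the same investigators enrol, grade and attribute every event.* Section 12.1d assigns relatedness only, to the Principal Investigator or a designee. Section 12.1c names no grader, and nothing says that the principal investigators enrol each subject.
- *A reader might infer that the monthly safety review opens the blind.* Section 13.6 makes it aggregate and blinded.

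It is also fair that tight balance has value in a trial of 30, where 2:1 was chosen to secure enough active recipients. That supports short blocks, but not a single printed size. A mix that includes 3s stays short and, in the cases worked above, removes the certainty.

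**Conclusion.** The point holds as a conditional weakness of the design, and it is an inexpensive improvement to make. Given one known placebo subject, or two known doxycycline subjects, in a complete block, the remaining assignments in that block are certain. The corresponding figures in a block of 6 are 80% and 50%.

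This rests on staff knowing entry order and stratum, which is likely at one centre but not stated, and on an initial recognition, whose frequency the documents do not allow anyone to estimate. The last block in a stratum may be incomplete and reveal fewer subjects.

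A reader might go on to infer that the primary result is biased. The documents do not support that. They do not say whether the grade 2 or higher count requires relatedness. If it does not, causality judgements do not enter it, and an effect through grading is an inference. Neither the direction nor the size of any bias can be stated.

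**What to change.** Keep 2:1 and the smoking strata. Generate the list with block sizes drawn at random from 3 and 6. Replace the sentence that gives the block size with one saying that permuted blocks of varying size are used and that the sizes are held only in the pharmacist's randomisation file.

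The cost is a new list and one edited sentence before the first subject. If enrolment has begun, the change can apply to blocks not yet started. The downside is a deviation of up to about 1.3 subjects per stratum instead of 0.7, and a possible doxycycline arm of 18 to 22 instead of 19 to 21. The change limits how far one recognition spreads; it does not prevent the recognition itself.

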#### Diagnosis and main criteria for inclusion:

#### Inclusion Criteria:

- 1. Males/Females ages 18-85 years
- 2. Documented HIV infection
- 3. CD4 cell count greater than 200 cells/mm3
- 4. HIV RNA less than 400 copies/ml
- 5. Stable antiretroviral therapy for greater than or equal to 12 weeks
- 6. Fulfills GOLD definition for COPD (post-bronchodilator FEV1/FVC less than 0.7) and/or has radiographic evidence of emphysema
- 7. Current or history of smoking with minimum 3 pack-year history
- 8. ALT and AST less than 3 x upper limit of normal
- 9. For women of childbearing potential: willingness to use 2 forms of birth control
- 10. Subjects on therapy for COPD must be on stable therapy for at least 4 weeks

#### Exclusion Criteria:

- 1. Pulmonary infection, COPD exacerbation, or acute opportunistic infection within 30 days of entry
- 2. Conditions associated with increased sedation of bronchoscopy risk, including but not limited to Gold class 3 or 4 COPD, requirement for home oxygen, hypercapneic respiratory failure, poorly control hypertension
- 3. Known allergy/intolerance to doxycycline, atropine, or any local anesthetic
- 4. Inability to provide informed consent
- 5. Pregnant or lactating women
- 6. Men must agree not to attempt to make a woman pregnant of participate in sperm donation during the study and for 6 weeks after discontinuing the drug
- 7. End stage renal disease
- 8. Cirrhosis
- 9. INR greater than 1.4
- 10. Platelets less than 80,000
- 11. Any condition including active drug or alcohol use or dependence that, in the opinion of the site investigator, would interfere with adherence to study requirements or increase the risk of bronchoscopy
- 12. Active or planned participation in any other clinical trial or observational study without prior approval from the PI

**Endpoints:** The primary endpoint will be safety/tolerability, and secondary endpoints will include change in pulmonary function (FEV1) by spirometry, inhibition of MMP activity in a pan-MMP activity assay as well as individual MMPs assessed by gelatinase assays and doxycycline levels in serum, epithelial lining fluid and bronchoalveolar lavage cell pellets (consisting of alveolar macrophages, lymphocytes and some neutrophils).

**Statistical Considerations:** The overall sample size is 30 subjects, all of whom will be recruited at WCMC. We anticipate screening 70 subjects to randomize 30. The study investigates the safety/ tolerability (grade 2 or higher toxicity) of long-term use of doxycycline. A 20-30% rate of grade 2 or higher toxicity is expected. With 20 doxycycline recipients, we will have approximately 80% power (one-sided alpha = 0.05) to detect a true proportion of 20% (grade 2 or higher toxicity) while rejecting the null hypothesis of 45.5% or higher (in other words, ruling out the possibility of the event rate being any higher that 45.5%). Below are additional scenarios based on a true proportion of 5- 40% (P1), which demonstrate power greater than 80% for n = 20 doxycycline recipients under these assumptions.

Data will be entered into the REDCap, a PHP-based system developed by Vanderbilt University and currently managed and updated through a national consortium that includes the Weill Cornell CTSC. In collaboration with the CTSC's data management group, we will create a secure, HIPAA-compliant, web-based study-specific database system with customized full field validation capabilities, a full audit trail and user-based privileges.

We will compute summary statistics (e.g. mean, median, SD, interquartile range, minimum and maximum) for demographic/clinical variables and the primary outcome data (e.g. spirometry endpoints, adverse events, biological endpoints, measurable doxycycline levels in serum and

ELF) by study arm. We will compare changes from baseline in continuous variables between the two groups by 2-sample t-tests or the non-parametric Wilcoxon's rank sum test as appropriate. We will perform repeated measures ANOVA or Multivariate ANOVA for repeated measures data (e.g. spirometry) as deemed appropriate after checking assumptions of sphericity using Mauchly's Test. Given the moderate sample size for this data we will compute confidence interval for estimates from RMANOVA or MANOVA to assess their precision. The proportions of subjects in each arm experiencing adverse events will be summarized by grade and compared by Chi-squared or Fisher's exact tests or generalized Fisher's test (using Monte Carlo approximations) as appropriate. In a pre-specified subgroup analysis, we will explore whether the subset of subjects with emphysema by CT respond differently to doxycycline compared to those without emphysema.

Our research groups have a strong record of recruiting HIV+ subjects into clinical trials and observational studies, and specifically of recruiting HIV+ subjects with emphysema into studies requiring bronchoscopies. The HIV clinics at the New York Presbyterian Hospital/Weill Cornell Medical Center follow approximately 2,500 active patients (defined as patients with clinic visits within the past 6 months. We are presently conducting an observational study to evaluate a screening strategy for COPD in our HIV clinics, consisting of a questionnaire and peak flow measurement (IRB # 0912010782). Subjects who meet specific criteria, and a random selection of controls who do not, will undergo Spirometry (pre- and post-bronchodilator) to assess for fixed airway obstruction. We anticipate that this study will lead to the identification of approximately 65 subjects with new diagnoses of COPD, in addition to the clinic patients with established diagnoses. Furthermore, [name] research group has independently identified a significant number of HIV+ subjects with COPD and a few with emphysema and no airflow obstruction who had come to volunteer for a research bronchoscopy study.

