## 7. INVESTIGATIONAL PLAN

#### 7.1. Endpoints

The primary endpoint will be safety/tolerability, and secondary endpoints will include change in pulmonary function (FEV1) by spirometry, inhibition of MMP activity in a pan-MMP activity assay as well as individual MMPs assessed by gelatinase assays and doxycycline levels in serum, epithelial lining fluid and bronchoalveolar lavage cell pellets (consisting of alveolar macrophages, lymphocytes and some neutrophils).

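### The trial is sized on a one-sample test of the doxycycline-arm toxicity rate against 45.5%, but the analysis text contains no matching analysis

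*Combined protocol and SAP*

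**What the plan says.** Section 7.1 states: "The primary endpoint will be safety/tolerability". The Statistical Considerations in the synopsis (Section 4) make this measurable: "The study investigates the safety/ tolerability (grade 2 or higher toxicity) of long-term use of doxycycline".

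The sample-size statement there concerns the doxycycline arm alone. With 20 recipients, "we will have approximately 80% power (one-sided alpha = 0.05) to detect a true proportion of 20" percent "while rejecting the null hypothesis of 45.5% or higher". It gives the intended conclusion as "ruling out the possibility of the event rate being any higher that 45.5" percent. The group, endpoint, null rate, alpha, direction and conclusion are therefore all stated.

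The analysis text follows in the same section. For adverse events, the proportions in each arm "experiencing adverse events will be summarized by grade and compared by Chi-squared or Fisher's exact tests", or by a generalized Fisher test. The only intervals it plans concern the repeated-measures data such as spirometry: "we will compute confidence interval for estimates from RMANOVA or MANOVA to assess their precision". Neither this text nor Sections 6, 7.1, 11 and 12 name a one-sample test, a confidence limit for the doxycycline-arm toxicity rate, or a critical number of events.

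**The concern.** The powered question is whether the toxicity rate on doxycycline is below a fixed value. The planned inference asks whether the two arms differ. A non-significant difference between 20 and 10 subjects does not show that the doxycycline rate is low, and a significant one does not show that it is high. A report that followed the analysis text to the letter would give a between-arm p-value for the primary endpoint and never state whether 45.5% was excluded. A reader could then take a non-significant p-value as reassurance when the criterion behind the sample size had failed.

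A smaller point concerns the boundary. The largest count that gives the stated power is 5 of 20. Whether 5 of 20 meets the criterion depends on how the bound is rounded and on the method used, and the method is not given in the available text.

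**Working it through.** **Inputs.** From the Statistical Considerations: n = 20 doxycycline recipients, null rate p0 = 0.455, true rate p1 = 0.20, one-sided alpha = 0.05. From the synopsis design: 30 subjects randomized 2:1, hence 20 and 10. All 20 recipients are assumed evaluable, because the plan gives no dropout allowance.

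**1. Reproduce the stated power.** Let X be the number of doxycycline recipients with grade 2 or higher toxicity. Reject p ≥ p0 if X ≤ c, where X is binomial(20, p).

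| c | P(X ≤ c) at p = 0.455 (alpha) | P(X ≤ c) at p = 0.20 (power) |
|---|---|---|
| 4 | 0.0169 | 0.6296 |
| 5 | 0.0505 | 0.8042 |
| 6 | 0.1207 | 0.9133 |

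The rule X ≤ 5 gives 80.4%, which is the plan's figure. The normal approximation with null variance gives 78.9% and the arcsine method 79.7%. The sizing is thus a one-sample test on the doxycycline arm, and its power is correct.

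**2. Find the bound for that rule.** The exact (Clopper-Pearson) one-sided 95% upper limit for x events in 20 is the 0.95 quantile of Beta(x + 1, 20 − x).

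- 4/20: 40.1%
- 5/20: 45.56%
- 9/20: 65.3%

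The 5/20 limit is the plan's 45.5% before rounding. At the printed value, P(X ≤ 5 | 0.455) = 0.0505, just above 0.05. At 45.6%, P(X ≤ 5 | 0.456) = 0.0496, just below it. So 5/20 passes an exact test against 45.6% and narrowly fails one against 45.5%.

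**3. Set the planned between-arm test beside the powered question.** The two-sided Fisher p-value is the sum of the hypergeometric probabilities no larger than that of the observed table.

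- 4/20 v 1/10 (5 events in 30): the observed table has probability 0.34. The only more probable table is 3 v 2, with probability 0.36. So p = 1 − 0.36 = 0.64.
- 9/20 v 2/10 (11 events in 30): the observed table has probability 0.1384. Adding the less probable tables, 0.0009 + 0.0106 + 0.0596 + 0.0338 + 0.0031, gives p = 0.25.
- 9/20 v 5/10: p = 1.0.

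| Doxycycline v placebo | Fisher p | Exact upper limit, doxycycline | 45.5% excluded? |
|---|---|---|---|
| 4/20 v 1/10 | 0.64 | 40.1% | yes |
| 9/20 v 2/10 | 0.25 | 65.3% | no |
| 9/20 v 5/10 | 1.0 | 65.3% | no |

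All three are non-significant between arms, but the powered question is answered differently in the first than in the other two.

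**The case against.** The strongest reply is that this is an omission and not a contradiction. The sample-size statement and the analysis text belong to one section, the hypothesis is fully declared there, and a between-arm comparison is compatible with it. The doxycycline proportion will be reported by grade, so a reader could compute the limit. This is a 30-subject pilot, and no go/no-go decision is tied to 45.5%. All of this is fair, and it limits the weight of the point. It does not supply the missing analysis: the plan says what it wants to rule out, and the only adverse-event inference it then specifies cannot do so.

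A second reply is that the sample-size statement announces further scenarios in a table that is not in the available text, and a note to that table might name the method. That is possible. The analysis text would still need to carry the method.

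Two stronger readings should be resisted.

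- A reader might infer that the power is really 63.0%, because an exact test at exactly 45.5% needs 4 or fewer events. The documents do not support this. They claim approximately 80%, and 45.5% is evidently 45.56% cut to one decimal. The apparent loss comes from a gap of 0.06 percentage points.
- A reader might infer that the choice of interval is decisive at 5/20, since Wilson (43.2%) and Wald (40.9%) limits exclude 45.5% and the exact limit does not. With the bound at 45.6%, all three exclude it, so this too reflects the rounding.

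**Conclusion.** The point holds, as a gap between what the trial is sized to show and what the analysis text will test. It should be fixed. The sample size and the stated power are not in error: 80.4% for 5 or fewer events in 20 at a true rate of 20%. What is missing is the analysis to which that power refers. The between-arm comparison cannot stand in for it, since it is non-significant both when 45.5% is excluded (4/20 v 1/10, upper limit 40.1%) and when it is not (9/20 v 2/10, upper limit 65.3%).

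The boundary issue is a rounding mismatch (45.56% printed as 45.5%; p = 0.0505 at 5/20). It needs reconciling because 5/20 is a plausible result, with probability 17.5% at a true rate of 20% and 17.9% at 30%, the ends of the plan's expected range. It is not an expected loss of power.

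The conclusion assumes 20 evaluable doxycycline recipients and, for the boundary figures, exact binomial methods. The absent scenario table could change which method is used. It would not remove the need to name that method in the analysis text.

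**What to change.** Add to the analysis text:

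> The proportion of doxycycline recipients with at least one grade 2 or higher toxicity will be reported with its exact (Clopper-Pearson) one-sided 95% upper confidence limit and compared with the null rate in the sample-size statement. The 80% power refers to this analysis. The between-arm chi-squared or Fisher comparison is supportive.

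In the sample-size statement, print the bound as 45.6% or give the rule as 5 or fewer of 20, so that the exact analysis and the stated power agree. If the scenario table names another method, use that method in the analysis text and make the bound agree with it.

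The cost is a few sentences and one figure or rule. No extra subjects, visits or data are needed, because the limit uses adverse-event data already collected. The downside is one more reported estimate and less weight on the between-arm p-value.

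### The sizing threshold of 45.5% is marginally too low for an exact analysis: 5 events in 20 recipients, which the quoted 80% power needs as a success, has an exact upper limit of 45.56%

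*Combined protocol and SAP*

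**What the plan says.** The only sizing of the primary safety endpoint is in the Synopsis (section 4), under Statistical Considerations. The plan first gives its expectation: "A 20-30% rate of grade 2 or higher toxicity is expected". It then states "With 20 doxycycline recipients, we will have approximately 80% power", with "one-sided alpha = 0.05", for a true rate of 20%, "while rejecting the null hypothesis of 45.5% or higher". It explains that rejection as "ruling out the possibility of the event rate being any higher that 45.5" per cent.

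This text names no test (exact, score or other) and no number of events that would count as success. It announces further scenarios for other true rates, but that table is not in the text available for this review, so any method shown there cannot be checked.

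The analysis paragraphs that follow in the Synopsis compare adverse event proportions between arms by chi-squared or Fisher-type tests. They do not mention the one-sample comparison used for the sizing.

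**The concern.** With 20 recipients the number of events is a whole number, so power moves in steps. The quoted power can be met only by one particular cut-off, and that cut-off should respect both the stated alpha and the stated threshold. Here it misses both by a hair.

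The outcome affected is 5 events in 20, an observed rate of 25%. That is the middle of the plan's expected 20-30% range, so it is not a remote case. If 5/20 were observed, whether 45.5% had been excluded would depend on the method chosen: an exact analysis says no, a score test says yes. Since the text does not name the method, that choice could be made after the data are known.

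**Working it through.** **Inputs**, all from the Synopsis, Statistical Considerations: n = 20 recipients; null rate p0 = 0.455; true rate p1 = 0.20; one-sided alpha = 0.05; stated power about 80%.

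**1. Reproduce the plan's figure by approximation.**

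Normal approximation, with null variance for the critical value and alternative variance for power:
- SE under the null = √(0.455 × 0.545 / 20) = 0.1114
- SE under the alternative = √(0.20 × 0.80 / 20) = 0.0894
- Power = Φ[(0.255 − 1.645 × 0.1114) / 0.0894] = Φ(0.80) = 78.9%

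Arcsine approximation:
- h = 2·arcsin√0.455 − 2·arcsin√0.20 = 0.553
- Power = Φ(0.553 × √20 − 1.645) = Φ(0.83) = 79.7%

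Both agree with about 80%.

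**2. Find the cut-off that the power implies.** With X binomial(20, p), a rule that declares success at c or fewer events has size P(X ≤ c | 0.455) and power P(X ≤ c | 0.20).

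| Success if events are | Exact size at 45.5% | Power at 20% | Exact one-sided upper 95% limit at c/20 |
|---|---|---|---|
| 4 or fewer | 0.0169 | 63.0% | 40.10% |
| 5 or fewer | 0.0505 | 80.4% | 45.56% |
| 6 or fewer | 0.1207 | 91.3% | 50.78% |

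Only the second row gives power near 80%. The step between the first two rows is the probability of exactly 5 events at a true 20%: 80.4% − 63.0%, or 17.5% before rounding (0.8042 − 0.6296 = 0.1746).

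**3. Test 5/20 against 45.5%.**
- Exact: P(X ≤ 5 | 0.455) = 0.01693 + 0.03361 = 0.05054, just above 0.05.
- The exact (Clopper-Pearson) upper limit is the p that solves P(X ≤ 5 | 20, p) = 0.05. This gives p = 0.45558, just above 45.5%.
- Score test: z = (0.25 − 0.455) / 0.1114 = −1.84, p = 0.033.
- Mid-p: 0.01693 + 0.03361 / 2 = 0.034.
- Continuity-corrected normal: p = 0.053.

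The exact and continuity-corrected tests do not reject; the score and mid-p tests do.

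**4. Change the threshold by one digit.** With p0 = 0.456, P(X ≤ 5 | 20, 0.456) = 0.0496, which is within alpha. The cut-off is still 5 and power at 20% is still 80.4%.

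**The case against.** The strongest reply is that nothing here is wrong at the precision the plan claims. It says approximately 80%, names no exact test, and its figure reproduces by two standard formulas. A score or mid-p test rejects 45.5% at 5/20. The excess in size is 0.0005, and the threshold is off by about 0.06 percentage points (45.56 − 45.5). All of this stands, and it keeps the point small.

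It does not remove the point. The score and mid-p tests use the same rule of 5 or fewer, so their true type I error at 45.5% is also 0.0505. No fixed cut-off keeps the true size at or below 0.05 and also gives 80% power against a 45.5% null.

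Three stronger readings are tempting and are not supported:

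- **That the trial has only 63% power.** That figure belongs to a strictly exact test at exactly 45.5%, which the documents do not specify. The drop comes from the discreteness of the binomial: moving from 5 to 4 events takes the attained size from 0.0505 down to 0.0169. A null of 45.6% recovers 80.4% with the same 20 recipients.
- **That a planned pass/fail verdict is compromised.** The 45.5% appears only in the sample-size justification. The analysis text sets no one-sample test and no go/no-go rule. That 45.5% is the 5/20 exact limit cut to one decimal is plausible, but the documents do not say how it was derived.
- **That the blocks of 3 within smoking strata force 19 or 21 recipients unless both strata are multiples of 3.** With 30 randomised and stratum remainders of 1 and 2, the complete blocks supply 18 recipients. The three leftover places supply exactly 2 more with probability (2/3 × 2/3) + (1/3 × 1/3) = 5/9, so 20 remains the most likely count. The only consequence for the plan is that any limit should be computed on the number actually treated.

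**Conclusion.** The combination of a 45.5% null, one-sided alpha 0.05 and about 80% power at n = 20 holds as an approximation and narrowly fails on an exact calculation: size 0.0505 against 0.05, and an exact limit of 45.56% against 45.5%. This is a minor error of precision in the threshold. It matters only at 5 of 20, an outcome with probability 17.5% if the true rate is 20%.

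The conclusion assumes exactly 20 evaluable recipients, independent events with a common rate, and one binary outcome per recipient (any grade 2 or higher toxicity). The binomial figures themselves are exact. The open question is which test the plan intends, and the available text does not say.

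**What to change.** In the Synopsis, Statistical Considerations:

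- Restate the null as 45.6% or higher. The rule of 5 or fewer in 20 then has exact size 0.0496 and power 80.4% at a true 20%.
- Define success as an exact one-sided upper 95% limit for the doxycycline arm below 45.6%. Add that this means 5 or fewer events if there are 20 recipients, and that the limit is computed on the actual number of recipients.

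The cost is one figure and one sentence. Sample size, randomisation and conduct are unaffected. The only downside is a threshold 0.1 percentage point less favourable (45.6% instead of 45.5%).
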